# 5.9 Discontinuation from Study

Patients may be removed from the study at any time if they meet any of the following criteria:

- Progression of disease\*
- Noncompliance with any part of the study, as evaluated by the Principal Investigator and Medical Monitor
- Patient request
- Withdrawal of consent
- Lost to Follow-up despite documented efforts at contact

- Clinically unacceptable adverse events despite optimal treatment or dose reduction.
- Death

\*Since study drug (either BBI608 or BBI503) targets cancer stem cells, patients may continue study drug (either BBI608 or BBI503) administration with or without sorafenib beyond progression per RECIST if the investigator concludes that the potential clinical benefits outweigh potential risks.

# **5.9.1** Dates Associated with Discontinuation from Study

The following clarifies important dates at the end of study treatment:

Date of Last Dose: The date that the last dose of study medication is taken (either BBI608 or

BBI503). The Date of Last Dose does not necessarily need to be the Date

Off Active Study.

Date Off Active Study: The date when both the patient and the investigator/study team understand

the patient to be off of active protocol treatment. In most cases, this will be the same as the *Date of Last Dose*; however, it does not need to be the case. In addition, the *Date Off Active Study* may not coincide with a formal study

visit.

End of Study Visit: A formal study visit held 14 to 30 days after the *Date of Last Dose*.

### 5.10 Follow Up After Treatment Discontinuation

For both the phase Ib and phase II portions of the study, the follow-up phase of the study will begin after the EOS study visit has been completed. Patients will be followed for specified clinical endpoints (both primary safety and secondary exploratory efficacy endpoint), and other important information such as post-protocol therapy.

As specified in Section 5.7.2, per-protocol imaging (every 8 weeks/56 days) should continue until criteria for disease progression according to both RECIST 1.1 and mRECIST for HCC are met.

There are no further visits required specifically for the study after the EOS visit, with the exception of radiologic assessments every 8 weeks until progression of disease is documented according to both RECIST 1.1 criteria and mRECIST for patients with HCC criteria.

The clinical parameters and endpoints for follow-up after a patient permanently discontinues study drug (either BBI608 or BBI503) administration are specified in table below, as is the recommended follow up frequency. Follow-up and information collection is intended to be accomplished through review of the local medical record system by site study staff and/or study CRAs-Monitors. Contact with the primary oncologist and/or primary care physician for a given patient may also be required.

Table 3: Clinical Parameters for Post-Protocol Therapy Follow-Up

Endpoint	Description	Follow-Up Frequency
Performance Status Decline	First date when ECOG performance status of $\geq 3$ is documented, if possible	Evidence for clinical endpoints
Subsequent Therapy	Names and dates of anti-cancer treatment administered after permanent study drug (either BBI608 or BBI503) discontinuation. "Clinical Trial" can also be used if agent name is not publically available	will be assessed monthly for the first 6 months after discontinuing study drug (either BBI608 or BBI503)  Then,  Quarterly from 6 months to 18
Objective Disease Progression following subsequent therapy	Date criteria for RECIST 1.1 and/or mRECIST for HCC categorization of "PD" are met after starting any post-protocol therapy, if possible*	months after discontinuing study drug (either BBI608 or BBI503)  Then,  Semi-annually thereafter
Survival	Date of death due to any cause	Semi-aminary mereaner

\*Passive follow-up only of radiologic imaging obtained following initiation of any post-protocol therapy

#### 6 STUDY PROCEDURES

# **6.1** Medical History

A complete medical history will be obtained. The components will include, but are not limited to, the following:

- Demography: date of birth, sex, race, ethnicity, height, and weight
- Clinically significant prior non-cancer diagnoses, surgeries, and current medications
- Prior cancer history, current cancer diagnosis, tumor stage at time of diagnosis and at time of study screening
- Prior surgical procedure(s), including date, anatomic site, and specific procedure performed; including loco-regional liver-directed therapy such as embolization, chemoembolization, radiofrequency ablation, etc.
- Current and prior modifiable risk-factors (smoking, alcohol use, including estimated amount and duration of use)
- Prior imaging reports, lesion measurements, and/or image reproductions may be requested from different periods in the cancer-specific history for a given patient.
- The suspected causal setting in which HCC arose is requested (i.e., a history of hepatitis C (HCV), hepatitis B (HBV), or inherited metabolic disorders).
- History of non-alcoholic fatty liver disease (NAFLD), if any
- Smoking and tobacco history
- In addition to AFP levels at baseline, at least one alfa-feto protein (AFP) level from before the baseline visit is requested, in order to establish two AFP levels prior to starting sorafenib on study.

Prior records, radiology reports, or procedure notes may be required in order to verify components of study patient history.

# 6.2 Physical Examination

Complete physical examination including height, weight, blood pressure, heart rate, respiratory rate, temperature (oral, axillary or tympanic) and ECOG performance status (Section 16). In addition, presence of encephalopathy and degree of ascites should be assessed so that Child Pugh score can be calculated.

### **6.3** Clinical Laboratory Tests

Safety laboratory determinations will include hematology, blood chemistry, and urinalyses. All laboratory tests required during the study must be obtained at a laboratory approved by the sponsor and site Principal Investigator. Please see the Laboratory and Procedure Manual for further details.

- Hematology: CBC including hemoglobin, hematocrit, white blood cell count with 5-part differential (automated differential is acceptable), red blood cell, platelet, INR (for prothrombin time).
- Blood chemistry: CO2, calcium, phosphorus, magnesium, albumin, glucose, and serum creatinine, AST, ALT, lactate dehydrogenase (LDH), alkaline phosphatase, total and direct bilirubin, uric acid, total protein and blood urea nitrogen (BUN), sodium, potassium, and chloride
- Routine urinalysis: dipstick and microscopy including protein, specific gravity, glucose and blood
- Serum pregnancy test for female patients of childbearing potential
- Serum alpha fetoprotein levels

Clinical Protocol BBI608-503-103HCC

### 6.4 Pharmacokinetic Assessments

### **6.4.1** Phase Ib

Pharmacokinetic assessments will be performed during the phase Ib portion of the study, and the schedule of assessments is based on the study arm the patient is assigned to.

### 6.4.1.1 Arm 1: BBI608

Plasma samples for pharmacokinetics will be obtained on Cycle 1, Day 15 and on Cycle 2, Day 15. Patients from selected sites may have overnight pharmacokinetic testing performed. The exact schedule of timepoints for all pharmacokinetic sampling can be found in the study Laboratory and Procedure Manual and is found in **Table 4** below.

Table 4: Complete Pharmacokinetic Sampling Schedule for Arm 1 (BBI608)

Cycle	Day	Procedure	Scheduled Time
1	15	ECG	Immediately before pre-dose sample
1	15	Draw blood sample	0 hr (pre-dose)
1	15	Patient is administered AM BBI608 dose	
1	15	Draw blood sample	0.5 hr (30 min)
1	15	Draw blood sample	1 hr
1	15	Draw blood sample	1.5 hr
1	15	Draw blood sample	2 hr
1	15	Draw blood sample	3 hr
1	15	ECG	$\sim 3.5 \text{ hr } (\pm 15 \text{ min})$
1	15	Draw blood sample	4 hr
1	15	Draw blood sample	6 hr
1	15	Draw blood sample	8 hr
1	15	Draw blood sample	10 hr
1	15	Draw blood sample	12 hr (pre-dose)
1	15	Patient is administered PM BBI608 dose	

2	15	Draw blood sample	0 hr (pre-dose)
2	15	Patient is administered AM BBI608 dose	
2	15	Draw blood sample	0.5 hr (30 min)
2	15	Draw blood sample	1 hr
2	15	Draw blood sample	1.5 hr
2	15	Draw blood sample	2 hr
2	15	Draw blood sample	3 hr
2	15	ECG	~ 3.5 hr
2	15	Draw blood sample	4 hr
2	15	Draw blood sample	6 hr
2	15	Draw blood sample	8 hr
2	15	Draw blood sample	10 hr
2	15	Draw blood sample	12 hr (pre-dose)
2	15	Patient is administered PM BBI608 dose	

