
# solely by RECIST 1.1 criteria or mRECIST criteria for patients with HCC, provided that the patient is obtaining potential clinical benefit in the opinion of the investigator. It is expected that most patients will receive between 4 and 24 weeks of treatment. **Pharmacokinetic** Pharmacokinetic variables to be determined include maximum plasma drug and concentration (Cmax), time to reach Cmax (Tmax), area under the time-**Pharmacodynamic** concentration curve (AUC), and terminal half-life. Variables: Blood samples for PK analyses will be performed on Cycle 1, Days 15-16 and on Cycle 2, Day 15 of the phase Ib portion. During the phase II portion, approximately six patients will collect PK as Phase I schedule, then a single pharmacokinetic blood draw may be obtained on Cycle 2, Day 15. Paraffin embedded tumor tissue is requested from all patients prior to initiation of protocol therapy. Patients may enroll if they do not have archival tissue. Patients may enroll if they are not aware if they have archival tissue. Pharmacodynamic studies as well as the concentration of study drug (either BBI608 or BBI503) in tumors will be examined following study drug administration in patients with accessible tumors who consent to an optional onstudy biopsy. This optional biopsy will be obtained on Cycle 2, Day 15. **Statistical Methods:** Statistics will be descriptive in nature, and formal sample size calculations were not performed. Phase Ib: Central randomization will be performed whereby patients will be assigned to Arm 1 (BBI608 plus sorafenib) or Arm 2 (BBI503 plus sorafenib) using block randomization. Each block will be considered a cohort with 3 subjects on Arm 1 and 3 subjects on Arm 2. After the first cohort for an Arm is complete, the dose level for the next cohort will be determined by the dose escalation rules. Safety will be summarized according to study arm. All patients receiving at least one dose of study drug (either BBI608 or BBI503) will be considered evaluable for safety analyses. Adverse events will be assessed according to CTCAE and will be evaluated by grade and organ class. Adverse event listings and tabulated summaries of categorized adverse events will be generated for all patients. Vital signs, laboratory data, and ECG data will be summarized for changes over time on study. The pharmacokinetic population will be all treated patients in a given arm with sufficient data to determine pharmacokinetic parameters. Phase II: Approximately 90 patients (30/arm) were planned to be randomized in 1:1:1 ratio into three treatment arms: Arm 1 (sorafenib plus BBI608), Arm 2 (sorafenib plus BBI503), and Arm 3 (sorafenib alone) before Amendment 3 was in effect. After amendment 3 was in effect. Arm 2 in the Phase II portion was closed for enrollment and randomization is conducted in a 1:1 ratio to the two remaining arms: Arm 1 and Arm 3. The targeted sample size remains 30 for Arm 1 and 30 Arm 3 after the amendment 3. There were approximately 10 subjects already enrolled in Arm 2 by the time amendment 3 was put into effect. Therefore, the total sample size of Phase II at the end of the trial is projected to be approximately 70 patients. Baseline characteristics as well as the observed safety, tolerability, and preliminary signs of anti-tumor activity will be summarized for each arm.

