- 11. Subjects with a history of another primary cancer, with the exception of: a) curatively resected non-melanoma skin cancer; b) curatively treated cervical carcinoma in situ; or c) other primary solid tumor with no known active disease present that, in the opinion of the investigator, will not affect patient outcome in the setting of current hepatocellular carcinoma diagnosis.
- 12. Abnormal ECGs which are clinically significant such as QT prolongation (QTc > 480 msec), clinically significant cardiac enlargement or hypertrophy, new bundle branch block, or signs of active ischemia. Patients with evidence of prior infarction who are NYHA functional classes II, III, or IV are excluded, as are patients with marked arrhythmias such as Wolff Parkinson White pattern or complete AV dissociation\*.
  - \*Patients with complete or incomplete AV dissociation who have a pacemaker may be eligible for enrollment provided they are NYHA functional class I: "No limitation of physical activity. Ordinary physical activity does not cause undue fatigue, palpitation, or dyspnea (shortness of breath)."

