# **5.4.3** Cycle 1, Day 15 | Start of Combination Therapy

The assessments on Cycle 1, Day 15 may be performed before, after, or both before and after the administration of study drug (either BBI608 or BBI503) as indicated below. Assessments performed before the administration of study drug are to characterize any objective effects of sorafenib monotherapy prior to the initiation of combination therapy.

For the phase Ib portion of the study, both sorafenib and study drug should be administered in clinic to accommodate pharmacokinetic evaluations. The administration schedule is according to study arm and is outlined in the study procedure manual.

For both the phase Ib and phase II portions of the study, the following C1D15 assessments should be performed *prior to the first dose of study drug* for patients randomized to receive either BBI608 or BBI503 in combination with sorafenib. If patients in Phase II have been randomized to receive sorafenib alone [Arm 3], the following labs are still required but may be obtained at any time on C1D15 (either before or after dosing with sorafenib on that day):

- Physical exam (including vital signs, weight)
- ECOG performance status (see Section 16)
- Hematology (see Section 6.3)
- Blood chemistry (see Section 6.3)
- Urinalysis (see Section 6.3)
- Electrocardiogram prior to first dose of study drug
- Serum AFP
- AE assessment
- Concomitant medications

After the above assessments are performed, study drug (either BBI608 or BBI503) may be initiated for those in the phase Ib portion of the study and for those in the Phase II portion who have been randomized to either [Arm 1] or [Arm 2\*]. For those patients administered a dose of study drug (either BBI608 or BBI503), the following assessments should be performed *after* receiving the dose:

- Phase Ib Only: Blood samples for pharmacokinetics (see Section 6.4).
- *Phase Ib Only:* Electrocardiogram pre dose and approximately 3.5 hours after the first dose of study drug (either BBI608 or BBI503) dispense 14-day supply of study drug (either BBI608 or BBI503)
- Dispense two (2) days of study drug (either BBI608 or BBI503) dosing to be kept as "extra doses" by patient during study in case of loss or issues with visit scheduling (see Pharmacy Manual)

The procedures above do not apply to those in the phase II portion who have been randomized to [Arm 3], sorafenib alone.

\* Once the amendment 3 is in effect, Arm 2 in the Phase II portion will be closed for enrollment.

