# Boston Biomedical, Inc September 12, 2017 Clinical Protocol BBI608-503-103HCC

### 14 APPENDIX A: SCHEDULE OF ASSESSMENTS - PHASE IB

Tarta O Dana and James	Pre-Study	Study Evaluations					E-1-604-1-372-24				
Tests & Procedures	Evaluation	Cycle 1 C			Cy	Cycle 2 Cycle 3+		End of Study Visit			
Week	0	1	2	3	3	4	1	3	1	3	14- 30 days from last
Day	0	1	8	15	16	22	1	15	1	15	dose of study drug
Window	-5 (+ 2) days		± 2 day	s			± 2	day	± 2	day	
Medical history	X										
Physical examination	X			X			X		X		X
Serum pregnancy test 	X										
ECOG performance status	X			X			X		X		X
Vital signs, Weight, Height 	X	X	X	X		X	X	X	X	X	X
Hematology	X			X			X		X		X
Blood chemistry	X			X			X		X		X
Urinalysis	X			X			X		X		X
Child Pugh Class assessment	X										X
12-Lead electrocardiogram	X			$X^3$				$X^{10}$			
Serum AFP	X			X			X		X		X
Optional Tumor biopsy	$X^4$							X 			
Pharmacokinetics				X	X 			X			
Concomitant medications	X	X	X	X		X	X	X	X	X	X
Adverse events		X	X	X	X	X	X	X	X	X	$\mathbf{X}^7$
Dispense BBI608 or BBI503				X 			X		X		
Schedule 8-week Scan		X									
Tumor Measurements &	At baseline and then at every 8 weeks (56 days, ±7) beginning with										
staging	Cycle 1, Day 1						$X^8$				

<sup>1For women of child-bearing potential (WOCBP)

<sup>2Height will be assessed at pre-treatment (baseline) only

<sup>3ECG will be done **twice** on this day—once before the first dose of study drug is administered, and once ~ 3.5 hours (± 15 min) after study drug is administered.

<sup>4The pre-treatment (Baseline) optional tumor biopsy may be performed at any time prior to the first sorafenib dose on Cycle 1 Day 1

<sup>5If the on-study biopsy is performed on a day other than a PK day, then a single blood draw is needed within 30 minutes of the biopsy

 $^6\mathrm{For}$  patients in Arm 2 (BBI503 + sorafenib) only

<sup>7 Patients who are identified at the EOS visit as having persistent adverse events related to study drug (either BBI608 or BBI503) should continue to be followed on a monthly basis (or more frequently if clinically indicated) until resolution of study drug-related adverse events or until the AEs are deemed irreversible.

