3. HYPOTHESES AND DECISION RULES

3.1. Statistical Hypotheses

There is no hypothesis testing in this study.

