Selected AEs were pre-specified for additional focus due to the potential clinical significance of the event and/or the potential association with the investigational product. These events include those in the standardized MedDRA query (SMQ) (narrow or broad, as noted):

Table 3 Adverse Events of Clinical Relevance SMQ Terms

MedDRA v19.0 Term	SMQ class
Ventricular fibrillation	NA (individual PT)
Ventricular tachycardia	NA (individual PT)
Non-infectious diarrhea	Broad
Gastrointestinal haemorrhage	Narrow

Gastrointestinal obstruction	Narrow
Acute kidney injury	Narrow (acute renal failure)

Tables listing the incidence, maximum severity, and drug relationship of these events in the safety population will be generated.

Adverse Events Leading to a Study Drug Discontinuation

Adverse Events leading to a study drug discontinuation will be identified based on any AEs collected on CRF End of Treatment page along with study drug hold action on Adverse Events page.

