7.2.4.3. Electrocardiograms

12-lead electrocardiogram (ECG) with categorical results (Normal, Abnormal [Not clinically significant], Abnormal [Clinically significant]) will be summarized. Shift tables showing results from baseline to worst post baseline will be provided. A patient listing will also be provided.

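### The SAP reduces the scheduled ECGs to a three-level reading shifted to the worst value, so no planned table shows QTc as a measured change or by time point

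*Protocol*

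**What the plan says.** **ECG schedule, Phase Ib.** Protocol 6.4.1.1 (Table 4) puts the first C1D15 ECG "Immediately before pre-dose sample" and a second at about 3.5 hours, between the 3-hour and 4-hour blood draws. Table 5 gives the same pair for BBI503. Appendix A agrees: "once before the first dose of study drug is administered, and once ~ 3.5 hours (± 15 min) after study drug is administered". Protocol 5.4.3 labels this pair as Phase Ib only: "Electrocardiogram pre dose and approximately 3.5 hours after the first dose of study drug". A further ECG follows on C2D15.

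**ECG schedule, Phase II.** Appendix B, footnote 11, asks for an ECG before BBI608 on C1D15 and after BBI608 on C2D15. Protocol 5.5.2 requires the C2D15 ECG in every arm and lets it move to C3D1 or later if dosing has been irregular.

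**Purpose.** Protocol 5.4.3 explains that the C1D15 assessments made before study drug are there to show what sorafenib alone has done.

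**QTc in the protocol.** It appears once, in exclusion criterion 12: "Abnormal ECGs which are clinically significant such as QT prolongation (QTc > 480 msec").

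**Planned analysis.** The synopsis (Statistical Methods, Phase Ib) states that "ECG data will be summarized for changes over time on study". SAP 7.2.4.3 states: "12-lead electrocardiogram (ECG) with categorical results (Normal, Abnormal [Not clinically significant], Abnormal [Clinically significant]) will be summarized". It adds a shift table from baseline to the worst later result and a patient listing whose content is not specified. SAP Table 3 names ventricular fibrillation and "Ventricular tachycardia" as events of clinical relevance. QT and QTc appear nowhere in the SAP.

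**The concern.** Safety and tolerability are primary objectives in both phases, and the pre-dose C1D15 ECG exists to mark the sorafenib background before the new drug is added. The planned table makes little use of that structure, for three reasons.

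- A category does not move when QTc rises within the range that a reader calls normal or not clinically significant.
- Taking the worst post-baseline category removes the time point, so the table cannot show change over time.
- The baseline is unclear. SAP 6.2 takes the last value before the first study drug dose without saying whether sorafenib counts. The protocol generally uses 'study drug' for BBI608 or BBI503. If the baseline is the pre-sorafenib ECG, the shift mixes sorafenib's effect with that of the added drug. In Arm 3 there is no study drug in the protocol's sense.

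The SAP also treats similar data differently: 7.2.4.2 and 7.2.4.4 plan numeric baseline values and maximum change for laboratory tests and vital signs, but 7.2.4.3 plans nothing numeric for ECGs. At stake is whether the report can put a number on any average QTc effect of adding BBI608 or BBI503 to sorafenib.

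**Working it through.** The plan has no QTc figure to reproduce. The check sets the collected ECGs beside the planned output, then asks what precision a numeric analysis could offer.

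**1. What could be computed, and what is planned**

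| ECG contrast | Who has it | Planned numeric summary |
|---|---|---|
| C1D15 pre-dose to about 3.5 h | Phase Ib; possibly the six Phase II napabucasin patients with full PK sampling (Protocol 6.4.2) | None |
| C1D15 pre-dose to C2D15 | Phase Ib, both arms | None |
| C1D15 to C2D15 or later visit | Phase II, including Arm 3 | None |
| Pre-study to C1D15 (sorafenib run-in) | Both phases | None |

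**2. Precision of a paired mean change in one group**

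Half-width of the 95% CI = t(0.975, n−1) × SD / √n. The documents give no SD of QTc change; 15 to 20 ms is assumed.

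- n = 3: 4.303 × 15/√3 = 37.3 ms; with SD 20, 49.7 ms.
- n = 6: 2.571 × 15/√6 = 15.7 ms; with SD 20, 21.0 ms.
- n = 12 (a dose level of six plus the optional six in Protocol 4.2): 9.5 to 12.7 ms.
- n = 30: 5.6 to 7.5 ms.

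The n = 30 result applies only to the Phase II change from C1D15 to C2D15. It does not apply to the pair around the first dose, which exists in Phase Ib cohorts of three to six.

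**3. Precision of the Phase II difference, Arm 1 minus Arm 3**

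Half-width = t(0.975, 58) × SD × √(2/30), with t = 2.002 and √(2/30) = 0.258.

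- SD 15: 2.002 × 15 × 0.258 = 7.8 ms.
- SD 20: 2.002 × 20 × 0.258 = 10.3 ms.

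This assumes that all 30 patients per arm have both ECGs. Drop-out before C2D15 widens it.

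**4. Why a count above a limit is not enough**

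Take QTc as normal with mean 420 ms and SD 20 to 25 ms, and a uniform rise of 20 ms (all assumed; truncation by the entry criterion ignored).

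- Before: P(Z > 60/20) = 0.1%; P(Z > 60/25) = 0.8%.
- After: P(Z > 40/20) = 2.3%; P(Z > 40/25) = 5.5%.
- Extra patients per 30: 30 × 0.022 = 0.7 to 30 × 0.047 = 1.4, so about one.

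Over means of 420 to 440 ms and SDs of 15 to 25 ms, the share above 480 ms is 0 to 5.5% before and 0.4 to 21% after. A uniform rise of this size would leave most patients below 480 ms. That limit is an entry criterion, not the SAP's definition of abnormal, so this does not measure how sensitive the shift table is.

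**5. Timing limits on any numeric analysis**

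- On C1D15 in Phase Ib both drugs are given in clinic (Protocol 5.4.3). In Arm 1, BBI608 comes first, with at least 2 hours before sorafenib, so the 3.5-hour ECG may follow that morning's sorafenib as well.
- Protocol 5.5.2 and Table 5 put the BBI503 C2D15 ECG about 13 hours after the night dose. Appendix A, footnote 10, says 3.5 hours without separating the arms. These passages must be reconciled.
- In Phase II the C2D15 ECG is at least 3.5 hours after BBI608; no clock time is set for Arm 3.

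**The case against.** The case for leaving the plan as it is has four parts.

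- **The study is descriptive.** SAP 3.1 says "There is no hypothesis testing in this study", and QTc is not an endpoint. This stands, but the request is for descriptive summaries, not a test.
- **A shift table is a summary of change, and the synopsis sentence sits under Phase Ib.** Both are true. The table is still coarse, and by collapsing to the worst value it does not show change over time.
- **Prolongation has other routes into the report.** A prolonged QT can be read as abnormal and enter the shift table. Reported as an adverse event, it appears by preferred term and grade, and in Phase Ib a related Grade 3 or 4 event can count as a dose-limiting toxicity. Ventricular tachycardia and fibrillation are tabulated separately. This stands and limits the point: what is missing is the measured change. These routes rely largely on open-label investigator judgement.
- **The eCRF is not among the documents.** If it records only the category, the SAP may simply match the data collected. This also stands. The exclusion criterion requires QTc to be read at screening, but it does not show that later values were entered.

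**Conclusion.** The point holds as a gap in SAP 7.2.4.3: no planned table gives QTc as a measured change or by time point. This falls short of the synopsis and is inconsistent with the numeric treatment of laboratory values and vital signs. It is an inexpensive improvement to a primary safety objective; it does not affect the efficacy results.

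A reader might infer three stronger things that the documents do not support.

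- **That any QTc rise would be invisible, or reported as no change.** Marked prolongation can still appear as an abnormal reading or an adverse event. What goes unquantified is a moderate average rise.
- **That the ECG pair around the first dose isolates the study drug with good precision.** The pair belongs to Phase Ib cohorts of three to six, where the half-width at n = 6 is about 16 to 21 ms, as large as a 20 ms effect. The later ECG may also follow sorafenib.
- **That Phase II gives a time-matched contrast with sorafenib alone.** It gives a concurrent control with a half-width of about 8 to 10 ms, but ECG times relative to dosing are not matched across arms.

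The precision figures rest on the assumed SD of change of 15 to 20 ms and on complete pairs.

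**What to change.** Amend SAP 7.2.4.3 as follows.

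- **Definitions.** Name the QT correction formula. Use the C1D15 pre-dose ECG as the reference, with the pre-sorafenib ECG as a second reference.
- **Phase Ib.** List and summarise QTc change to about 3.5 hours post-dose and to C2D15, by arm and dose level. State that cohorts of three to six give only coarse estimates, that the 3.5-hour ECG may follow sorafenib too, and that Table 5 sets the BBI503 C2D15 ECG at about 13 hours. Reconcile Appendix A, footnote 10, with Table 5.
- **Phase II.** Tabulate the change from C1D15 to C2D15, or to the later visit if the ECG was moved, for Arm 1 beside Arm 3. Give the between-arm difference with its 95% CI and report the actual ECG time relative to dosing.
- **Both phases.** Count patients above the protocol's 480 ms entry limit at each time point, and keep the categorical shift table as supportive.

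The cost is SAP wording and a small set of tables, with no new ECGs or visits. The downside is data capture: if the eCRF holds only the category, a QTc field must be added or the values taken from existing tracings. If they cannot be retrieved, the SAP and the study report should say that QTc effects were not evaluated.
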